## 15 EXPLORATORY ASSESSMENTS

Exploratory analyses of efficacy will include accepted spirometry values performed as per protocol and be based on the FAS, and on the PPS analysis populations (as sensitivity analysis)

### 15.1 Spirometry Measures

For the spirometry measures (FEV1 % predicted, FEV1/FVC, FEV1 absolute, FVC absolute, FVC % predicted), the observed values and corresponding changes from baseline will be summarized using descriptive statistics by parameter and visit. Different methods of measuring will not be distinguished in the descriptive statistics and the statistical model. Baseline spirometry measurement is the last post-bronchodilator assessment at randomization visit (Visit 1) prior to inhalation of IMP which is the following measurement in the eCRF: Before inhalation of IMP (“Before inhalation of 2-4 puffs of salbutamol” if “Before inhalation of IMP” is not available).

For each spirometry measure identified in Section 8.5, treatment group comparisons will be carried out using a mixed model for repeated measures (MMRM), using all available measurements of the outcome of interest. The dependent variables will be the absolute change from baseline of the outcome of interest at the visits scheduled for Weeks 2 through 12, using fixed effects for treatment, visit, and the treatment x visit interaction and the baseline value as a fixed effect covariate. Treatment group comparisons at each visit will be estimated by differences between the marginal (adjusted) means from the treatment x visit interaction, with accompanying p-values and 95% confidence intervals. The analyses will include pairwise treatment group comparisons for each post-baseline visit via contrasts.

For the covariance model of the MMRM analyses, an unstructured covariance matrix should preferably be used. If the model does not converge (e.g., due to the small sample size), a Heterogeneous Toeplitz matrix will be used and, if this model does not converge either, a compound symmetry matrix will be used. If all models fail to converge, patients treated with L-CsA 2 x 5 mg/day or 2 x 10 mg/day will be merged into one group that will be compared to placebo, and the models for the covariance matrix will be applied as before, starting with an unstructured matrix, until the model converges. If none of the models converge, treatment group

comparisons of change versus baseline will be performed for each visit using pairwise, independent samples t-tests on the observed data. Note that the covariance model to be used may be different for different spirometry parameters, depending on whether and when convergence is achieved.

Descriptive summary measures will be provided based on all observed values as well as based on the marginal means determined via MMRM analyses (if convergence can be achieved).

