5 INTRODUCTION

5.1 Bronchiolitis Obliterans Syndrome

Bronchiolitis obliterans (BO) (also called obliterative bronchiolitis) is a progressive lung disease affecting the bronchioles. It is widely believed to be a sequela of injury or damage, and BO is usually diagnosed months to years following injury. Recognized forms of injury that predispose to the occurrence of BO include allograft rejection in lung transplantation, graft vs host disease in hematopoietic cell transplantation [Au 2011], respiratory infections, or environmental or chemical exposure [Aguilar 2016]. Lung allografts are particularly susceptible to BO as a result of acute rejection in addition to the other described risk factors [Meyer 2014]. BO is irreversible and leads to respiratory failure.

Although the pathogenesis of BO is not well understood, histopathologic findings of constrictive bronchiolitis, airway distortion, and subepithelial fibrosis are thought to be the result of post-injury inflammatory infiltrates leading to an abnormal cytokine response and subsequent accumulation of fibroblasts with fibroproliferation [Aguilar 2016].

The main histologic hallmark of BO is scarring with fibrosis of the airways. Because of difficulties with histologic diagnosis, the clinical manifestation of BO, bronchiolitis obliterans syndrome (BOS), was defined as irreversible airway obstruction, diagnosed by pulmonary function, in the absence of other causes. This diagnosis does not require histologic confirmation but is considered a reliable surrogate physiologic marker of the presence of BO [Estenne 2002].

In patients with BOS, the major findings on spirometry are a reduced forced expiratory volume in 1 second (FEV₁), a normal or slightly decreased forced vital capacity (FVC), and a reduced ratio of FEV₁ to FVC, with poor response to inhaled bronchodilators consistent with a fixed obstructive airway disease. Lung volumes indicate air trapping, with a normal total lung capacity and high residual volume. However, a subset of patients presents with a restrictive pattern characterized by a low FVC and a normal FEV₁/FVC ratio, or a mixed pattern of obstruction and restriction [Barker 2014].

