10.1.4 Other Medication

All inhaled medications, except investigational inhaled medications, are permissible during the trial.

Patients on bronchodilators should be on a stable dose 4 weeks prior to randomization and throughout the study. All other inhaled medication should be administered after spirometry in the following order: inhaled corticosteroids, inhaled antifungals/antibiotics, and then inhaled IMP. For details with regard to spirometry measurements, please refer to [Section 11.1.1](#).

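### SAP 15.1 defines baseline spirometry as post-bronchodilator but allows an unmatched pre-salbutamol fallback, so a change computed from a fallback baseline can contain the bronchodilator response

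*SAP*

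**What the plan says.** The baseline rule is in SAP 15.1: "Baseline spirometry measurement is the last post-bronchodilator assessment at randomization visit (Visit 1) prior to inhalation of IMP". The SAP identifies this with the eCRF measurement made before IMP inhalation. If that is not available, it uses the measurement labelled "Before inhalation of 2-4 puffs of salbutamol".

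The preceding sentence reads: "Different methods of measuring will not be distinguished in the descriptive statistics and the statistical model".

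On the outcome of the mixed model, SAP 15.1 says: "The dependent variables will be the absolute change from baseline of the outcome of interest at the visits scheduled for Weeks 2 through 12". Its terms are treatment, visit, their interaction and baseline; none is for bronchodilator status. It applies the model to the spirometry measures listed in SAP 8.5, namely FEV1 % predicted and FEV1/FVC. Absolute FEV1, absolute FVC and FVC % predicted are only summarized descriptively.

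On bronchodilators, Protocol 10.1.4 says: "Patients on bronchodilators should be on a stable dose 4 weeks prior to randomization and throughout the study". On the remaining inhaled products, the same section adds: "All other inhaled medication should be administered after spirometry in the following order", and the list that follows runs from inhaled corticosteroids to IMP. Protocol 5.1 describes the spirometry of BOS as "with poor response to inhaled bronchodilators consistent with a fixed obstructive airway disease".

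**The concern.** A value taken before salbutamol does not meet the SAP's own definition of baseline. The fallback nevertheless enters the analysis as baseline, both as the value subtracted and as the covariate, with nothing to mark it. Where the value before the change and the value after it were taken under different bronchodilator conditions, the change mixes any treatment or disease effect with the response to the bronchodilator.

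With 8 patients per arm, one such patient is an eighth of the arm mean. At stake are the exploratory FEV1 % predicted and FEV1/FVC comparisons and the descriptive changes in the other spirometry measures.

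**Working it through.** **Inputs**

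- Patients per arm: n = 8 (SAP 9.2).
- Mismatched patients in an arm: not given; assumed 1 or 2, with 4 as an extreme.
- Bronchodilator response b: not given; assumed 50, 100 or 200 mL for FEV1, or 4 points for FEV1 % predicted.

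The plan has no figure of its own to reproduce. The sample size rests on feasibility, with no effect size or SD.

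**Step 1: does anything match follow-up to baseline?**

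- Protocol 11.1.1 (spirometry method) does not mention salbutamol.
- Protocol 13.2.3 (Visits 2 to 5) lists spirometry without a bronchodilator condition.
- Protocol 10.1.4 puts inhaled medication other than bronchodilators after spirometry. This implies that bronchodilators come first, but it is not stated as a rule.
- SAP 10.2.2 says only that baseline spirometry precedes IMP.
- The per-protocol sensitivity analysis (SAP 15) is not built around this issue.

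So nothing does.

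**Step 2: which patients are mismatched, and in which direction?** Assume that follow-up has one bronchodilator status for all patients.

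| Follow-up | Regular baseline (post) | Fallback baseline (pre) |
|---|---|---|
| Post-bronchodilator | 0 | +b |
| Pre-bronchodilator | −b | 0 |

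**Step 3: size in one arm.** With m mismatched patients, the arm's mean change shifts by m × b / 8 in absolute size.

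| Assumed b | m = 1 | m = 2 |
|---|---|---|
| 50 mL | 50/8 = 6.25 mL | 12.5 mL |
| 100 mL | 12.5 mL | 25 mL |
| 200 mL | 25 mL | 2 × 200/8 = 50 mL |
| 4 points of % predicted | 4/8 = 0.5 point | 1.0 point |

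The last row is on the scale of a modelled endpoint. FEV1/FVC is left out because numerator and denominator can both rise after a bronchodilator, so neither size nor sign follows from b.

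**Step 4: between arms.** Let arms A and B have kA and kB fallback patients.

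- Post-bronchodilator follow-up: kA × b/8 − kB × b/8 = (kA − kB) × b/8.
- Pre-bronchodilator follow-up: −(8 − kA) × b/8 + (8 − kB) × b/8 = (kA − kB) × b/8.

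The unadjusted contrast is the same in both cases: the arm with more fallbacks looks better. If kA = kB it is zero. The within-arm changes are still shifted, unless follow-up is post-bronchodilator and there are no fallbacks, or follow-up is pre-bronchodilator and every baseline is a fallback.

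**Step 5: does the baseline covariate remove the shift?** An ANCOVA of change on treatment and baseline was simulated with 8 patients per arm and 4,000 runs. Assumptions: between-patient SD 12 and within-patient SD 4 points of % predicted, b = 4 points, post-bronchodilator follow-up, and all fallbacks in one arm.

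| Fallbacks in one arm | Arithmetic shift | Simulated bias | 95% CI coverage |
|---|---|---|---|
| 0 | 0 | 0.01 | 94.5% |
| 1 | 0.5 | 0.44 | 95.1% |
| 2 | 1.0 | 0.90 | 94.3% |
| 4 | 2.0 | 1.73 | 92.0% |

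About 87 to 90% of the shift remains after adjustment. If no covariance model converges, the t-tests named as the last resort in SAP 15.1 have no baseline covariate and carry all of it.

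**The case against.** The case for leaving the rule alone has several parts, and much of it stands.

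- **It may never arise.** The effect needs at least one mismatched pair. If follow-up is post-bronchodilator, that means at least one fallback patient, and the documents do not show that there will be any.
- **The direction is open.** A reader might infer that the rule favours apparent improvement. That requires post-bronchodilator follow-up, which Protocol 10.1.4 implies at most. Otherwise the fallback patients are the correctly matched ones.
- **The primary assessment is untouched.** A reader might infer that the rule could hide a fall in FEV1 in the primary tolerability analysis. It cannot act there through this baseline: SAP 13.1 identifies the Change in FEV1 item from adverse-event preferred terms with onset within 1 hour of inhalation. The affected analyses are exploratory, and Protocol 14 treats all p-values as descriptive.
- **The response may be small.** Protocol 5.1 describes poor bronchodilator response in BOS, and active asthma is excluded.
- **Between-arm bias cancels in expectation.** Baseline spirometry precedes the first dose and is listed ahead of randomization (Protocol 13.2.2), so fallback use should not depend on treatment. With one or two fallbacks in one arm, simulated coverage stays close to 95%.
- **The sentence on methods is ambiguous.** It might be read as a decision to pool pre- and post-bronchodilator values. It may only mean equipment, since each site uses its own (Protocol 11.1.1). The model has no bronchodilator term on either reading.

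A reader might also set the shift in mL against the earlier trial's slope difference: 0.037 L/month × 84/30.4 months = about 0.10 L over 12 weeks. That trial was in lung transplant recipients, and FEV1 in litres is not a modelled endpoint here, so the ratio says little about this trial.

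These points limit the consequence. They do not reconcile the definition with its fallback or supply a matching rule.

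**Conclusion.** The point holds in a limited form. The SAP defines one kind of baseline, admits another, and neither matches follow-up to it nor adjusts for the difference. This is a stated rule that can mix unlike measurements, so it is more than a missing detail. The documents do not support saying that changes already contain the bronchodilator response, or that the mean change is biased in a known direction.

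The size rests on assumed inputs: about 6 to 50 mL in an arm's mean FEV1 change for one or two mismatched patients and a response of 50 to 200 mL, or 0.5 to 1.0 point of % predicted for a response of 4 points. With pre-bronchodilator follow-up, most patients would be mismatched and the within-arm shift would be larger and downward. Between arms, the bias averages zero over randomizations. In a single unstratified trial of 24 patients, an uneven split of fallbacks is possible, and the baseline covariate would remove little of the result. Severity is low.

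**What to change.** Amend SAP 15.1 before database lock:

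1. State the bronchodilator status of the spirometry value used at each visit, and use the same status at baseline and follow-up wherever both are recorded.
2. Report the number of fallback baselines by arm.
3. Add a sensitivity run of the mixed model that excludes patients whose baseline and follow-up do not match.
4. Allow a Screening value as a substitute baseline only if its bronchodilator status is documented and matches. It can be up to 4 weeks older than Visit 1, and the protocol does not state its status.
5. Say what the sentence on different methods of measuring covers.

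Keeping mismatched patients in the main model and excluding them only in the sensitivity analysis avoids losing anyone from arms of 8. A patient without a baseline has neither change scores nor the covariate, and would drop out of that model at every visit. The cost is SAP wording, one count table and one extra model run, with a slightly smaller n in the sensitivity analysis.

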# 9 STATISTICAL CONSIDERATIONS

## 9.1 General Considerations and Descriptive Statistics

Analyses and outputs will be produced using SAS® software PPD, version 9.4 or later, or other suitable, commercially or publicly available statistical software, in a secure and validated environment. All tables, figures and data listings to be included in the report will be independently checked for consistency and integrity.

The data recorded in the eCRF will be summarized as appropriate, per treatment group and for the applicable total analysis population, using the following descriptive measures:

- All continuous assessments will be summarized using descriptive statistics (i.e., n, mean, standard deviation, median, Q1, Q3, minimum, and maximum).
- All categorical assessments will be summarized by using frequency counts and percentages.
- Discrete ordinal or higher-level data will be summarized as continuous data, but a tabulation of categories may also be included, depending on the number of categories.
- “Missing” category should be added for a categorical variable if there is at least one subject with missing data for that categorical variable unless the following evaluation requires otherwise.

For all measures analyzed, tabulations comparing the treatment groups will be prepared. For outcomes measured more than once, the analyses will include tabulations of the measured values

---

by visit, as well as change from baseline. Where provided, all confidence intervals will be two-sided 95% intervals.

All data recorded in the eCRF will be listed in subject data listings.

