## 15.2 Short Form (36) Health Survey (SF-36)

The SF-36 is a multi-purpose, short-form health survey with 36 questions yielding 8 health domain scales and 2 psychometrically based physical and mental component summary measures. The standard form of the SF-36 Version 1 will be used and the raw data (questions), the scoring of health domains and the summary scores will be provided in SAS Format to Biostats by Data Management. The calculation of the derived scores will be done by validated CCI System.

The 8 health domain scales are referred to as the ‘Physical Functioning (PF)’, ‘Role- Physical (RP)’, ‘Bodily Pain (BP)’, ‘General Health (GH)’, ‘Vitality (VT)’, ‘Social Functioning (SF)’, ‘Role-Emotional (RE)’, and ‘Mental Health (MH)’ scales. The two summary measures are referred to as the physical component score (PCS) and mental component score (MCS).

For the scales and summary scores of the SF-36, the numeric values and corresponding changes from baseline will be summarized using descriptive statistics by parameter and time point.

The analysis will be carried out using a mixed model for repeated measures (MMRM), using all available measurements of the outcome of interest. The dependent variables will be the absolute change from baseline of the outcome of interest at the visits scheduled for Weeks 2 through 12, using fixed effects for treatment, visit, and the treatment x visit interaction and the baseline value as a fixed effect covariate. Treatment group comparisons in the change versus baseline at each visit will be estimated by differences between the marginal (adjusted) means from the treatment x visit interaction, with accompanying p-values and 95% confidence intervals.

Descriptive summary measures will be provided based on all observed values as well as based on the marginal means determined via MMRM analyses.

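### If the spirometry MMRM falls back to plain compound symmetry and the spread of change grows over time, Week 12 intervals are too narrow and Week 2 intervals too wide

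*SAP*

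**What the plan says.** SAP 15.1 models repeated spirometry measures as follows: "The dependent variables will be the absolute change from baseline of the outcome of interest at the visits scheduled for Weeks 2 through 12". The model's fixed terms are treatment group, visit, their interaction and baseline. Treatment differences are reported at each visit "with accompanying p-values and 95% confidence intervals". SAP 9.1 adds: "Where provided, all confidence intervals will be two-sided 95% intervals".

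The covariance sequence has three steps before the treatment arms are altered:

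1. "an unstructured covariance matrix should preferably be used".
2. On failure, "a Heterogeneous Toeplitz matrix will be used".
3. Then, "if this model does not converge either, a compound symmetry matrix will be used".

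If all three fail, the two L-CsA doses are merged and the sequence is repeated. If that fails too, t-tests are done visit by visit. The SAP names no sandwich standard error and no degrees-of-freedom method.

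For SF-36, SAP 15.2 says: "The analysis will be carried out using a mixed model for repeated measures (MMRM), using all available measurements of the outcome of interest". It gives no covariance structure and no fallback for the eight scales and two summary scores. Protocol 14.2.4 gives the same fixed effects, names no covariance structure and leaves the detail to the SAP.

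**The concern.** The SAP attaches the word heterogeneous to the Toeplitz step and not to compound symmetry. The natural reading of step 3 is therefore the ordinary form, with one variance and one correlation across all four post-baseline visits. Every other step lets the variance differ by visit, including the final t-tests.

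If the spread of change from baseline widens as time passes, a single pooled variance lies below the true one at Week 12 and above it at Week 2. The model-based interval at the end-of-treatment visit would then look more precise than it is, and the Week 2 interval less precise. In a descriptive trial with 8 patients per arm, the intervals are the main guide to uncertainty. SAP 15.1 also lets the covariance model differ between spirometry parameters, so FEV1 % predicted and FEV1/FVC could be reported under different variance assumptions.

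**Working it through.** **Inputs from the documents.** Three arms of 8, so 3 x 8 = 24 (SAP 9.2). Four post-baseline visits, the fixed effects above, and two-sided 95% intervals. The sample size rests on feasibility, so there is no stated SD, power or interval width to reproduce.

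**Assumed inputs.** By-visit SDs, correlations and missingness. Neither document gives any of these.

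**Covariance parameters with 4 visits.**
- Unstructured: 4 x 5 / 2 = 10.
- Heterogeneous Toeplitz: 4 variances + 3 correlations = 7.
- Heterogeneous compound symmetry: 4 variances + 1 correlation = 5.
- Compound symmetry: 1 + 1 = 2.

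The SAP goes from 7 to 2 in one step.

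**Standard error ratio.** With complete balanced data, compound symmetry estimates the mean of the visit variances. So at visit t:

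model SE / true SE = sqrt(mean of SD²) / SD_t

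For SDs of 4, 5, 6.5 and 8, the mean variance is (16 + 25 + 42.25 + 64) / 4 = 36.81 and the pooled SD is 6.07. The ratio is 6.07 / 8 = 0.76 at Week 12 and 6.07 / 4 = 1.52 at Week 2. Ignoring the baseline adjustment, the SE of a two-arm difference is SD x sqrt(2/8) = SD x 0.5. The model would report 3.03 at both visits, where the true values are 4.0 at Week 12 and 2.0 at Week 2.

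**Two-sided error.** The large-sample value is 2 x [1 − Φ(1.96 x ratio)]. The simulated values come from fitting compound symmetry to trials with no true effect.

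| SDs at Weeks 2, 4, 8, 12 | Growth | Ratio, Week 2 | Ratio, Week 12 | Large-sample error, Week 2 / 12 | Simulated error, Week 2 / 12 |
|---|---|---|---|---|---|
| equal | x1 | 1.00 | 1.00 | 5% / 5% | about 5% / 5% |
| 5.3, 5.7, 6.2, 6.6 | x1.25 | 1.13 | 0.90 | 2.7% / 7.6% | about 2.4% / 7% |
| 5, 5.5, 6.5, 7.5 | x1.5 | 1.24 | 0.83 | 1.5% / 10.5% | about 1.6% / 10% |
| 4, 5, 6.5, 8 | x2 | 1.52 | 0.76 | 0.3% / 13.7% | about 0.4% / 14% |

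A separate simulation with linear SD growth (6000 runs per scenario, correlation 0.5 and 0.8) agrees. Week 12 coverage of the 95% interval was about 92%, 89.5% and 86% for growth of 1.25, 1.5 and 2. It was about 95% at every visit with no growth.

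**Effect of visit-specific variances.** Setting: SD doubling, correlation 0.6, about 15% missing at each of Weeks 4, 8 and 12, 733 runs.

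| Model | Coverage at Weeks 2 / 4 / 8 / 12 |
|---|---|
| Compound symmetry | 99.9 / 98.8 / 94.4 / 87.0% |
| Heterogeneous compound symmetry | 94.0 / 95.5 / 95.8 / 95.1% |

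**How often the step is reached.** In those 733 runs the unstructured model always converged. A further REML check used SD growth of 1.5 and autoregressive correlation 0.7. The missing rate applies to Weeks 4 and 8 and was lower at Weeks 2 and 12. The convergence criterion is also an assumption, and SAS may behave differently.

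| Patients | Missing | Both first steps failed |
|---|---|---|
| 24 | 15% | 0 of 300 |
| 18 | 30% | 13 of 188 (7%) |
| 12 | 30% | 54 of 126 (43%) |

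Heterogeneous compound symmetry met the criterion in all 13 + 54 = 67 double failures. Over all runs, Week 12 coverage for compound symmetry against the heterogeneous form was 92.7% and 96.7% with 24 patients, 93.6% and 95.2% with 18, and 91.3% and 91.3% with 12. In the smallest case the heterogeneous form brought no gain, so the degrees-of-freedom method matters too.

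**The case against.** The case against acting is substantial, and most of it stands.

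- **Reaching the step.** A reader might infer that the SAP expects non-convergence. It does not: it mentions small sample size as an example of why a model might fail, and two structures with visit-specific variances come first. Weeks 2 and 12 are mandatory on-site visits (Protocol synopsis). What remains is that Visits 3 and 4 may be remote and the schedule shows no remote spirometry, only accepted spirometry values are used, the analysis is repeated in the PPS (SAP 15), and randomized patients are not replaced (Protocol 9.3.3).
- **Meaning of the error rates.** A reader might take 7% to 14% as the error of the SAP's procedure. It is the error of compound symmetry fitted to every simulated dataset, not only to those where the earlier steps failed.
- **Growing spread.** Widening of change from baseline is plausible, but neither document shows it. With constant spread, compound symmetry is correct.
- **Consequence.** Spirometry is exploratory (SAP 8.5), p-values are descriptive (Protocol 14), type I error control does not apply (SAP 9.3), and Week 12 has no stated priority over the other visits. By-visit SDs will be tabulated, so unequal spread would be visible beside the model output.
- **Remedy.** Deleting plain compound symmetry would bring the merging of the two doses closer and could lose the 5 mg against 10 mg comparison. This is a good reason to add a step, not to remove one.

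The missing SF-36 covariance structure and degrees-of-freedom method are separate gaps in detail. They do not depend on growing spread, and they do not prove it.

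**Conclusion.** The point holds conditionally, as a minor one. Three things must coincide: both earlier structures fail, step 3 means the one-variance form, and the spread of change grows over time. Then, for SD growth of 1.25 to 2 times, the Week 12 standard error is about 10% to 24% too small. A nominal 5% error is about 7% to 14% at Week 12 and about 2.5% to 0.5% at Week 2.

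The direction follows from algebra; the size rests on assumed SDs. The documents do not support saying that the Week 12 results will be wrong. At full enrolment with modest missingness the step is unlikely to be used, and the primary tolerability and safety assessments and the PK analysis are untouched.

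**What to change.** In SAP 15.1, insert heterogeneous compound symmetry (5 parameters) between heterogeneous Toeplitz and compound symmetry. Keep plain compound symmetry as the last three-arm model, so that the L-CsA doses are not merged any sooner than now. The SAP repeats the sequence after merging, so the added step carries over. State Kenward-Roger degrees of freedom for the MMRM. In SAP 15.2, refer to the same sequence for the ten SF-36 outcomes.

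The cost is a sentence in 15.1, a cross-reference in 15.2, a few lines of code and one more model in the sequence. Week 12 intervals will be wider when the new step is used and spread grows.
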